7.3. Vital Signs, Weight, Height

Body weight, height and vital signs variables including respiratory rate, blood pressure (systolic and diastolic), and temperature will be measured at visits as per the time and events schedule in the protocol. Descriptive statistics of the observed value and change from baseline of the vital signs through Week 16 will be summarized by treatment group for Part 1. Box plots of vital signs and change from baseline through Week 52 will be provided.

Physical exam findings will not be analyzed except that they are captured as AEs and are included in the analyses of AEs.

7.4. Other Safety Parameters

7.4.1. Suicidal Ideation and Behavior

The Columbia-Suicide Severity Rating Scale (C-SSRS) will be used as a screening tool to prospectively evaluate suicidal ideation and behavior in children and adolescents ≥ 6 to < 18 years of age. The C-SSRS is an investigator-administered questionnaire that defines 5 subtypes of suicidal ideation and four possible suicidal behaviors, as well as non-suicidal self-injurious behavior (NSSIB) and completed suicide. There are 4 versions of the C-SSRS will be used in this study; a baseline version for children ≥ 6 to < 12 years of age, a Baseline/Screening version for adolescents ≥ 12 years of age, a Children's Since Last Visit version will be completed at all other visits, and a Since Last Visit version for adolescents. The 'Baseline' and 'Baseline/Screening

version of the C-SSRS will be conducted at Screening followed by the Since Last Visit version of the C-SSRS at all other visits through the end of the study.

The C-SSRS will be performed during each evaluation visit according to the assessment schedule and should be performed after the CDLQI and before any other study procedure. Participants will be interviewed by the investigator or study site personnel in a private, quiet place.

In addition, potential suicide related adverse events including suicidal ideation, suicidal behavior excluding completed suicide, self-injurious behavior, and completed suicide will be identified by the investigators and collected in the eCRF.

The following are C-SSRS categories and have binary responses (yes/no). A “yes” response to any C-SSRS category will be assigned a score as below:

Suicidal Ideation (1-5)

1 = Wish to be Dead

2 = Non-specific Active Suicidal Thoughts

3 = Active Suicidal Ideation with Any Methods (Not Plan) without Intent to Act

4 = Active Suicidal Ideation with Some Intent to Act, without Specific Plan

5 = Active Suicidal Ideation with Specific Plan and Intent

Suicidal Behavior (6-10)

6 = Preparatory Acts or Behavior

7 = Aborted Attempt

8 = Interrupted Attempt

9 = Actual Attempt (non-fatal)

10 = Completed Suicide

If no events qualify for a score of 1 to 10, a score of 0 will be assigned (0=“Negative result [no suicidal ideation or behavior]”). Higher scores indicate greater severity.

Subjects with any suicidal ideation, suicidal behavior, or self-injurious behavior will be listed.

7.4.2. Injection Pain

Pain experienced with each placebo or guselkumab injection will be assessed at each study visit at which an injection is administered. Injection pain will be assessed using the Faces Pain Scale-Revised (FPS-R) for children ≥ 6 to <12 years of age, and the linear Injection Pain Visual Analog Scale (VAS) for adolescents ≥ 12 to <18 years of age.

The FPS-S evaluates how much pain subjects experienced with the injection. The score ranges from 0 to 10, with score of 0 shows “no pain” and score of 10 shows very much pain. The VAS evaluates injection pain by placing a vertical mark on the line (100 mm in length from 0 of no injection pain to 100 of very much pain). A trained observer will measure the distance in millimeters (0-100) from the left of the scale to the participant’s mark.

Descriptive statistics of FPS-R and VAS including mean, SD, median, minimal, and maximal will be summarized by visit and study intervention received.

7.4.3. Head Circumference

Descriptive statistics of head circumference and change from baseline will be summarized at Week 0 and Week 52 for participants ≥ 6 to < 12 years of age.

7.4.4. Tanner Staging

Count and percentage of tanner scale (range from stage 1 to stage 5) will be summarized by gender and age group.

8. PHARMACOKINETICS/PHARMACODYNAMICS

8.1. Pharmacokinetics

Blood samples for measuring serum guselkumab concentrations (pre-injection if it is an injection visit) will be collected from all subjects at scheduled visits as indicated in the Time and Events schedule in the protocol.

The PK analysis will be based on subjects who received at least 1 administration of guselkumab and had at least one evaluable PK blood sample for serum guselkumab concentration. No imputation of missing concentration data will be performed, that is, data summaries will be based on the observed data.

All concentrations below the lowest quantifiable sample concentration of the assay (BQL) or missing data will be labeled as such in the concentration data listings or Statistical Analysis System (SAS) dataset. The BQL concentrations will be treated as zero in the summary statistics.

For the analysis of serum guselkumab concentrations, descriptive statistics, including arithmetic mean, SD, median, interquartile range, minimum, and maximum will be calculated, where appropriate, at each scheduled sampling time point by treatment group. The PK concentration data may be displayed graphically. The following analyses will be performed by treatment group if appropriate:

- In Part 1, serum guselkumab concentrations will be summarized for the following periods.
 - From Week 0 through Week 16 for all subjects randomized and treated with guselkumab by age (6 to < 12 , 12 to < 18 years), baseline weight (< 70 , ≥ 70 kg), and overall;
 - From Week 0 through Week 44 by visit for subjects treated with guselkumab .
 - Subjects randomized to placebo → guselkumab and guselkumab (who are PASI 90 non-responders at Week 16)
 - Subjects randomized to etanercept → guselkumab (who initiated treatment with guselkumab at Week 20)

- Subjects randomized to guselkumab (who are PASI 90 responders at Week 16): From Week 0 through the time of retreatment with guselkumab. Serum guselkumab concentration will be excluded after retreatment.
 - Summary of serum guselkumab concentrations at the time of retreatment with guselkumab for subjects randomized to guselkumab who were PASI 90 responders and withdrawn from guselkumab at Week 16.
- In Part 2, serum guselkumab concentrations from Week 0 through Week 44 will be summarized by age (6 to <12, 12 to <18 years), baseline weight (<70, ≥70 kg), and overall for all subjects treated with guselkumab
- If needed, serum guselkumab concentrations from Week 0 through Week 16 will be summarized for all subjects treated with guselkumab (Part 1 and Part 2 combined).

All summaries for serum guselkumab concentration will exclude data collected after subjects (1) did not receive a scheduled guselkumab administration within ± 14 days of the protocol scheduled dosing date; (2) discontinued study agent administration; (3) received a partial, incorrect, or an additional guselkumab administration (ie, subjects received more than 1 guselkumab injection within the scheduled guselkumab injection window); or (4) received an increased or decreased dose due to body weight change (eg, from the initial category of <70 kg to the category of ≥ 70 kg or vice versa) for the concentration summaries by baseline weight. Of note, serum guselkumab concentrations prior to the first of such events will be included in the summaries. All subjects and samples excluded from the analysis will be clearly documented.

In addition, invalid concentration data will be excluded from analysis. A concentration will be considered invalid (1) if a sample prior to guselkumab injection was actually taken after guselkumab administration (based on date/time); or (2) a concentration value fell outside the predefined statistical range of mean $\pm 10 \times \text{SD}$ of the concentration values obtained at the same protocol specified sampling timepoint (refer to SOP-07948-GXP, Version 2.1).

If there were multiple samples collected prior to an injection, the closest sample before the injection will be used. If a sampling time or an injection time was missing, the date will be used. If sampling date was the same as the injection date, the sample will be included in the statistical summary.

A population PK analysis using a nonlinear mixed-effects modeling approach will be used to characterize the disposition characteristics of guselkumab in the current study. Data may be combined with those of other selected studies to support a relevant structural model. The CL/F and V/F values will be estimated. The influence of important variables (such as body weight and age) on the population PK parameter estimates will be evaluated. Details will be given in a population PK analysis plan and results of the population PK analysis will be presented in a separate technical report.

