## 6. STUDY INTERVENTION

### 6.1. Study Interventions Administered

Designation	Product	
Investigational Medicinal Product(s)	Guselkumab Authorization status in the EU/EEA:	
	Authorized	
	Unauthorized	X
	Placebo Authorization status in the EU/EEA:	
	Authorized	
	Unauthorized	X
	Etanercept Authorization status in the EU/EEA:	
	Authorized	X
	Unauthorized	

Guselkumab or placebo will be administered SC using a sponsor-supplied, single use administration device. This will be either the CCI PFS assembled with the UltraSafe Plus™ Passive Needle Guard (PFS-U) device, designed to deliver a single, fixed dose of CCI, or a CCI. Identical devices containing placebo will be used to deliver a volume equivalent to that of active treatment for participants randomized to the placebo arm. Guselkumab will be supplied as a CCI solution of guselkumab in a single-use CCI or CCI PFS. The PFS-U is assembled with a PFS containing 1.0 mL of study intervention and the CCI.

Participants will receive a dose based on body weight. At each dosing visit, participant weight will be measured and the dose of guselkumab will be adjusted accordingly. Participants will receive 1 of the following dose levels depending on their weight:

- Weight <70 kg: CCI administered CCI
- Weight ≥70 kg: CCI administered using the PFS-U

Placebo for guselkumab will also be supplied in a PFS assembled with either the UltraSafe Plus™ Passive Needle Guard or the CCI. Participants who weigh <70 kg will receive 1 or 2 injections of either guselkumab or placebo with a volume(s) determined using the weight-based dose calculation for guselkumab. In Part 2 of the study, participants or their caregiver will be given the option to self-administer guselkumab at the study site. Participants must be ≥12 years of age to self-administer guselkumab.

Commercially available etanercept (25 mg powder and solvent for solution for injection and 50 mg prefilled syringes) will be supplied and administered subcutaneously based on body weight:

- <63 kg: 0.8 mg/kg once weekly using powder and solvent for solution for injection.
- ≥63 kg: 50 mg once weekly administered using a prefilled syringe.

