Participants receiving etanercept or their caregiver will also be given the option to self-administer study injections either at the study site when a visit is scheduled or at-home for doses required between regular visits. Participants who weigh <63 kg will receive 1 or 2 injections with a volume(s) determined using the weight-based calculation for etanercept.

Study staff will receive training on study intervention administration using either PFS-U or CCI, which must be documented. For participants/caregivers who will self-administer, training on study intervention administration will be provided by study staff. This will include education regarding instructions for use (IFU), proper handling and storage of devices, guidance on study intervention injection, and proper handling and accounting for used devices. Required storage conditions and expiration date are indicated on the label.

At any time, if participants or caregivers are uncertain about how to administer the study intervention or have questions regarding self-administration, the sponsor recommends that study staff review the IFU with the participant/caregiver along with practice injections with a training device if necessary. Patients or caregivers may be retrained at any time during the study, including if there is a use issue reported by the patient or caregiver. If at any time there is a change in the device required for dosing (eg, CCI to PFS-U) due to a change in a participant's body weight, and the participant/caregiver wishes to continue with self-administration, they must receive training on the new device and the participant/caregiver using the device must be witnessed self-administering a successful injection by study staff prior to performing self-administration.

Different sites should be used for consecutive injections or for two injections administered on the same day. Sites that are tender for any reason should be avoided. Study intervention and injections of other concomitant medications should be given at different anatomic sites.

Details on dose preparation and administration can be found in the Study Site Investigational Product Procedures Manual.

## Part 1

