Part 2 of the main study will be an open-label, single-arm study to collect additional efficacy, safety, and PK data for pediatric participants with a continuous weight-based dose regimen of guselkumab at Weeks 0, 4, and q8w thereafter through Week 52. Participants ≥ 12 to < 18 years of age will begin enrollment in Part 2 after the reviews of safety and PK data through Week 16 for all participants ≥ 12 to < 18 years of age in Part 1a have been completed, and an appropriate body weight-based dose that matches adult exposure has been confirmed, or a revised body weight-based dose has been determined. Enrollment of participants ≥ 6 to < 12 years of age into Part 2 will not occur until all participants in Part 1b have completed 16 weeks of treatment and all efficacy data through Week 16 from Part 1 have been evaluated by the sponsor, and all available safety data have been reviewed by an independent DMC. Part 2 will enroll enough additional participants to achieve a total of at least 100 participants exposed to guselkumab (ie, at least 10 participants in Part 2, with the total number dependent on the number of participants randomized in Part 1 who are exposed to guselkumab).

In Part 2 of the main study, participants will be given the option to self-administer or have their caregiver administer study injections at the study site using the appropriate presentation (either a prefilled syringe (PFS) assembled with the UltraSafe Plus™ Passive Needle Guard (PFS-U) device, designed to deliver a single, fixed dose of CCI or a PFS assembled with the CCI which delivers CCI. Depending on body weight, participants using the CCI may need to administer up to 2 injections using 2 devices. Participants must be at least 12 years of age to self-administer study injections. Participants or their caregivers will be trained on proper use of the device(s) and deemed capable, as determined by a health care provider (HCP). Otherwise injections will continue to be performed by a HCP.

All participants who complete either Part 1 or Part 2 of the main study through Week 52 will be offered the opportunity to participate in an open-label LTE. Participants will be required to return to the study site every 8 weeks for safety and efficacy assessments in addition to study intervention administration. The LTE will continue until approval for guselkumab in pediatric psoriasis is obtained or the development of the guselkumab pediatric plaque psoriasis indication is discontinued.

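### SAP 8.1 glosses an additional guselkumab administration as more than one injection in the window, so a correct two-injection dose below 70 kg would, read literally, remove later concentrations from the descriptive PK summaries

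*SAP*

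**What the plan says.** SAP Section 8.1 sets the scope of the rule: "All summaries for serum guselkumab concentration will exclude data collected after subjects" meet any of four listed events. The third event is that a participant "received a partial, incorrect, or an additional guselkumab administration (ie, subjects received more than 1 guselkumab injection within the scheduled guselkumab injection window". The section then limits the effect: "serum guselkumab concentrations prior to the first of such events will be included in the summaries".

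On how a dose is given, Protocol Section 6.1 states: "Participants who weigh <70 kg will receive 1 or 2 injections of either guselkumab or placebo with a volume(s) determined using the weight-based dose calculation". It also gives an instruction for the two-injection case: "Different sites should be used for consecutive injections or for two injections administered on the same day". SAP Section 1.2, describing Part 2, says that depending on body weight a participant using the device for the lower weight group "may need to administer up to 2 injections using 2 devices". From 70 kg upwards, Protocol Section 6.1 assigns the prefilled syringe that delivers one fixed dose.

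SAP Section 8.1 plans concentration summaries by age group, by baseline weight below and from 70 kg, and overall. They cover Part 1 through Week 16 and Part 2 through Week 44. Further Part 1 summaries cover PASI 90 non-responders, etanercept crossovers, and responders up to and at retreatment.

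**The concern.** The explanatory clause in the third event counts injections. The regimen it is applied to does not fix the number of injections per dose. A participant whose scheduled dose needs two injections, and who receives both as planned, satisfies the clause on the first day of guselkumab. Everything sampled afterwards is then flagged as collected after a dosing error that did not occur.

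The loss would not be random. Body weight determines who needs a second injection, and weight is one of the factors by which the concentrations are to be summarised. After baseline, the summary for participants below 70 kg would describe only those dosed with one injection, and the by-age and overall summaries would be thinned in the same selective way. Pharmacokinetics is a secondary objective, and these tables are its direct description.

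The fourth event in the same list was written with weight-based dosing in mind, since it handles a change of weight category. The third event was not.

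**Working it through.** The plan gives no figure to reproduce. The check applies the rule as written to the scheduled samples.

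**Inputs**

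- PK sampling weeks in the Schedules of Activities for Part 1 and Part 2: 0, 4, 12, 16, 20, 28, 36 and 44, which is 8 samples. Protocol Table 1 agrees: 2 PK-only plus 6 PK-and-immunogenicity samples = 8.
- Etanercept participants have no PK draw at Weeks 0, 4 and 12 (Part 1 Schedule of Activities, footnote z). That leaves Weeks 16, 20, 28, 36 and 44, which is 5 samples.
- Samples at dosing visits are taken before the injection (SAP 8.1), so the sample at the first two-injection visit precedes the event and is kept.
- First guselkumab dose: Week 0 in the guselkumab arm and in Part 2; Week 16 for placebo participants who are PASI 90 non-responders; Week 20 for etanercept participants who continue.

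**Rule applied**

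Let *f* be the week of the first two-injection dose. A sample at week *w* is kept if *w* ≤ *f* and dropped if *w* > *f*.

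| Participant | *f* | Kept | Dropped |
|---|---|---|---|
| Guselkumab arm, summaries through Week 16 | 0 | Week 0 (1 of 4) | Weeks 4, 12, 16 |
| Part 2, or guselkumab-arm PASI 90 non-responder, through Week 44 | 0 | Week 0 (1 of 8) | Weeks 4, 12, 16, 20, 28, 36, 44 |
| Placebo, PASI 90 non-responder, switched at Week 16 | 16 | Weeks 0, 4, 12, 16 (4 of 8) | Weeks 20, 28, 36, 44 |
| Etanercept, switched at Week 20 | 20 | Weeks 16, 20 (2 of 5) | Weeks 28, 36, 44 |
| Guselkumab arm or Part 2, first needs two injections at Week 12 (illustrative) | 12 | Weeks 0, 4, 12 (3 of 8) | Weeks 16, 20, 28, 36, 44 |

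In the first four rows every kept sample was taken before any guselkumab, so no post-exposure concentration survives. In the last row the Week 4 and Week 12 values survive.

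**How many participants**

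This cannot be computed. The weight at which a second injection is needed is redacted, and neither document gives a weight distribution. The planned Part 1 guselkumab arm is 30 (Part 1a) + 10 (Part 1b) = 40, so the possible range there is 0 to 40. Crossover and Part 2 participants would add to it.

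**The case against.** The strongest reply is that the clause only explains the words before it, and those words concern an additional administration. The documents often use *injection* for a dosing event: SAP 8.1 speaks of an injection visit, an injection time and an injection window, and Protocol Section 4.2 refers to the last guselkumab injection at Week 44. In that sense the rule excludes a second dosing event within one window, which is reasonable. The planned summaries for participants below 70 kg also suggest that nobody meant to discard them. This stands as an account of the likely intent. It does not settle the text, because Protocol 6.1 and SAP 1.2 also use the word for single device uses, and the clause is worded as a definition with no exception. A programmer who follows it loses valid data; one who follows the presumed intent departs from the SAP without a record.

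Two stronger readings are tempting, and the documents support neither. A reader might infer that these participants vanish from every concentration summary. They do not: values before the first event are kept, so they still count at Week 0, at all pre-switch visits for crossovers, and at earlier visits for anyone who moves to two injections later. A reader might also infer that the comparison of paediatric with adult exposure is compromised. That comparison rests on modelling and simulation under a separate interim analysis plan, and weight and age effects are assessed by population PK under its own plan. Nothing in SAP 8.1 applies this exclusion to those datasets.

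It is also fair to say that the error is recoverable. The samples are still taken, dosing is recorded, and SAP 8.1 requires every exclusion to be documented, so a wrong flag would be visible and the tables could be rerun.

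**Conclusion.** The rule is wrong as written, with moderate severity. Under its literal reading, a participant on two injections from the first guselkumab dose contributes no post-exposure concentration to the descriptive summaries: in the guselkumab arm, 1 of 4 scheduled samples is kept through Week 16, and for Part 2 participants and PASI 90 non-responders 1 of 8 through Week 44. The post-baseline by-weight, by-age and overall tables would then be selected by body weight.

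This rests on two conditions: that *injection* in the clause means one device use, and that at least some participants below 70 kg need two. The protocol and SAP plainly provide for the second, but its frequency is unknown (0 to 40 in the Part 1 guselkumab arm at the planned minimum enrolment). The direction of any distortion cannot be stated either. Efficacy, safety, type 1 error and power are untouched.

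**What to change.** Reword the third event so that it refers to the dose rather than the number of injections, for example:

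> (3) received a partial or incorrect guselkumab dose, or a guselkumab administration beyond the scheduled weight-based dose. One or two injections that together make up one scheduled dose count as one administration.

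The per-protocol definition in SAP Section 2.4.1.2 already takes this approach, since it refers to extra administrations and not to injections. The cost is one sentence in the SAP and one change to the PK exclusion flag. No dose, schedule or data collection changes. If any concentration tables have already been produced, check which reading the flag used and rerun them if it counted injections.

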#### 4.3. Justification for Dose

In the guselkumab Phase 3 studies CNTO1959PSO3001 and CNTO1959PSO3002 in adult participants with moderate to severe plaque psoriasis, the dose and dosing regimen of guselkumab CCI SC at Weeks 0, 4, and q8w thereafter, produced high levels of efficacy and a favorable benefit:risk profile across the entire adult study population. In addition, an association between systemic exposure to guselkumab and clinical responses (IGA and PASI) was observed. Since adult and pediatric plaque psoriasis share similar clinical manifestations, histological features, genetic factors, and treatment options, it is reasonable to assume that pediatric participants who attain similar systemic exposure to guselkumab will likely exhibit similar clinical responses as observed in the adult population. Therefore, the goal for selection of the dose and dosing regimen in the proposed guselkumab pediatric plaque psoriasis study was to achieve exposure in the pediatric population similar to the exposure attained in the adult plaque psoriasis study population.

CCI  
[REDACTED]  
[REDACTED]  
[REDACTED]  
[REDACTED]  
[REDACTED]  
[REDACTED]. Therefore, dose selection for this pediatric study was based on body weight only, typical for systemic therapeutic biologics administered in pediatric patients.

Pharmacokinetic simulations were performed to select an appropriate dose for pediatric participants that would achieve similar systemic exposure to guselkumab as seen in the adult Phase 3 studies. The results from these simulations suggested that the dose regimen of guselkumab CCI SC at Week 0, 4, and q8w thereafter, which has been approved for use in adults with moderate to severe plaque psoriasis, would achieve a guselkumab exposure in pediatric participants with body weight  $\geq 70$  kg similar to that achieved in adult participants. For pediatric participants with a body weight  $< 70$  kg, several weight-based dose regimens (in mg/kg) were simulated to identify the regimen that would achieve consistent guselkumab exposures across age groups and weight ranges in the pediatric population. The results from these simulations suggested that a dose regimen of guselkumab CCI at Weeks 0, 4, and q8w thereafter in pediatric participants weighing  $< 70$  kg would achieve an exposure comparable to that observed for adult participants.

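### SAP 8.1 exclusion (4) is worded more broadly than its evident purpose: read literally, it drops later PK samples from adherent, growing children in the <70 kg summaries by baseline weight

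*SAP*

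**What the plan says.** SAP 8.1 lists four events after which concentrations leave the summaries. The fourth is that a subject "received an increased or decreased dose due to body weight change". A parenthesis opened by *eg* follows, describing a move "from the initial category of <70 kg to the category of" 70 kg or more, or the reverse. This criterion applies only "for the concentration summaries by baseline weight". The section adds that "serum guselkumab concentrations prior to the first of such events will be included in the summaries".

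Two summaries by baseline weight (<70, ≥70 kg) are planned. In Part 1 the summary runs from Week 0 through Week 16. In Part 2, "serum guselkumab concentrations from Week 0 through Week 44 will be summarized by age", by baseline weight and overall.

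On dosing, Protocol 6.1 states: "At each dosing visit, participant weight will be measured and the dose of guselkumab will be adjusted accordingly". Participants below 70 kg receive one or two injections "with a volume(s) determined using the weight-based dose calculation for guselkumab". Protocol 4.3 reports that for this group "several weight-based dose regimens (in mg/kg) were simulated"; the regimen chosen is redacted. At 70 kg and over, the prefilled syringe with needle guard (PFS-U) delivers one fixed dose.

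**The concern.** Below 70 kg, a dose that rises because the child has grown is adherence to the protocol. Such a dose is nevertheless an increased dose due to body weight change, so it meets criterion (4) as written. Only a move across 70 kg changes the regimen and makes the baseline-weight label wrong, and that is the sensible reason for having the criterion.

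The effect falls on one row. Growth within the ≥70 kg category leaves a fixed dose unchanged. Growth within the <70 kg category can trigger exclusion at any dosing visit after Week 0. At later visits the <70 kg row would consist increasingly of children whose calculated dose had not changed, set beside a ≥70 kg row with no such selection. These tables are the plan's direct descriptive view of whether the two weight regimens give similar concentrations. Two programmers could also derive different datasets from the same sentence.

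**Working it through.** The plan states no figure to reproduce here. The check is of wording, followed by an illustration of size.

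**Wording.** The operative words of criterion (4) cover any dose change due to weight. The example does not narrow them. In the same list, criterion (3) uses *ie* where it explains its own terms. Protocol 6.1 makes dose adjustment possible at every dosing visit. A dose change within <70 kg therefore satisfies both the protocol regimen and the SAP exclusion.

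**Inputs from the documents.** PK samples are drawn before dosing.
- Part 1: doses at Weeks 0, 4, 12; post-baseline samples to Week 16 at Weeks 4, 12, 16 (three).
- Part 2: doses at Weeks 0, 4 and every 8 weeks; post-baseline samples at Weeks 4, 12, 16, 20, 28, 36, 44 (seven).

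**Assumptions, not in the documents.** Steady growth of g = 2 or 6 kg a year; a dose step equivalent to s = 1, 2.5, 5 or 7 kg of body weight (the true step is redacted); starting weight at a random point within a step; no visit-to-visit weight fluctuation, which would add to the loss.

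**Formulas.** Gain by week t: G(t) = g × t/52. Chance that the dose has changed by week t: min(1, G(t)/s). A sample is dropped if a changed dose was given at an earlier visit, so a pre-dose sample at the visit of change is kept.
- The Week 16 sample in Part 1 depends on G(12) = 0.46 kg (g = 2) or 1.38 kg (g = 6).
- The Week 44 sample in Part 2 depends on G(36) = 1.38 kg or 4.15 kg.
- Part 1 share of samples lost: the chances at Weeks 4 and 12, summed and divided by 3.
- Part 2 share of samples lost: the chances at Weeks 4, 12, 12, 20, 28 and 36 (for samples at Weeks 12, 16, 20, 28, 36, 44), summed and divided by 7.

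Results for the <70 kg row, g = 2 to g = 6:

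| Step s | Children losing Week 16 (Part 1) | Samples lost, Part 1 | Children losing Week 44 (Part 2) | Samples lost, Part 2 |
|---|---|---|---|---|
| 1 kg | 46–100% | 21–49% | 100% | 55–78% |
| 2.5 kg | 18–55% | 8–25% | 55–100% | 25–60% |
| 5 kg | 9–28% | 4–12% | 28–83% | 12–37% |
| 7 kg | 7–20% | 3–9% | 20–59% | 9–26% |

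Worked example, s = 1, g = 6, Part 1: (0.46 + 1)/3 = 49%. A simulation with weights rounded to 0.1 kg agrees within about two percentage points.

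**Limiting case.** With near-continuous dosing (0.1 kg steps), even 2 kg a year gives G(4) = 0.15 kg, so every growing child has a changed dose at Week 4. The loss is then 2 of 3 samples in Part 1 (67%) and 6 of 7 in Part 2 (86%).

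**After the fix.** For assumed starting weights of 20 to 65 kg, the heaviest child reaches 65 + 4.15 = 69.15 kg by Week 36 at 6 kg a year. None crosses 70 kg and no sample is lost. At that growth rate, only children starting within about 1.4 kg below 70 kg (Part 1) or 4.2 kg below (Part 2) would be affected.

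**The case against.** The best defence is that the context shows what was meant. The parenthesis speaks of an initial category and the reverse move, and the criterion is confined to tables split at 70 kg. Protocol 6.1 lists exactly two dose levels, so a changed dose could mean a move between them. The SAP also uses *eg* loosely: SAP 5.5.2.1 introduces the two defined loss-of-response criteria with it, although they are the full set. This stands as evidence of intent, and crossing 70 kg is probably what the authors had in mind. It does not make the sentence say so.

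The limits on consequence also stand. Only the descriptive summaries by baseline weight are touched, and no test between the rows is planned. Comparability with adult exposure is judged by PK modelling and simulation. The population PK analysis, which evaluates body weight, has its own plan. SAP 8.1 requires excluded subjects and samples to be documented, so an over-broad application should be visible.

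A reader might infer more than the text supports. One inference is that whole children are excluded; they are not, because earlier samples stay in. Another is that the <70 kg row would end up holding only children who did not gain weight. With a coarse dose step many growing children keep the same dose: at 5 kg steps, 72% to 91% would still contribute the Part 1 Week 16 sample.

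**Conclusion.** The wording of criterion (4) is broader than its evident purpose and should be narrowed. Applied literally, it would selectively thin the later samples in the <70 kg row, in Part 1 to Week 16 and in Part 2 to Week 44, and leave the ≥70 kg row largely intact.

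The size of the loss cannot be determined from the documents. The illustration runs from a few percent to most of the later samples, and it depends on the assumed growth rate and dose step.

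It may be tempting to conclude that the trial's finding on exposure comparable to adults is compromised. The documents do not support that, because the modelling does not depend on these tables. No efficacy, safety or Type I error conclusion is affected either. Severity is minor. Confidence is moderate, because the intended meaning was probably the narrower one.

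**What to change.** Reword criterion (4) so that, for the summaries by baseline weight, data are excluded only after a participant's weight moves between the <70 kg and ≥70 kg categories relative to baseline and the dosing regimen changes with it. Changing *eg* to *ie* would do most of this. Add one sentence stating that protocol-specified dose recalculation within the <70 kg category is not an exclusion.

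If tables have already been produced, the study report should say which reading was programmed.

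The cost is one SAP phrase and one sentence. No dose, visit or sample changes, there are fewer exclusions to derive, and valid concentrations are kept.
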